[figure not shown]

Impact Of Post-Bariatric Body Contouring Procedures on Patient Body Weight and Metabolism

NCT05034081

Date of document 2\3\2026

[School]
[Course title]

Patients and methods

This is a prospective comparative study on 60 patients will be conducted on post-bariatric patients seeking for body contouring surgery from 2021 to 2025.

The primary contouring procedures will be analyzed including panniculectomy, abdominoplasty, and lower body lift. Brachioplasty, mastopexy with breast reduction or augmentation, arm and thigh lift, liposuction, facelift, and pubic/genital plasty procedures were identified and considered as “other procedures.”

Weight of the resected tissue will be recorded. Patient demographic characteristics included age, gender, and body mass index (BMI) both before and at the last available follow-up visit after bariatric surgery. Thorough patient co-morbidity assessments were performed. This cohort of patients was then matched and compared with a 1:1 control group of patients who had only undergo for bariatric surgery. Matching will be based on age, gender, BMI at the time of bariatric surgery, type of bariatric surgery procedure, and length of follow-up.

These patients will be divided into 2 groups. Group (A): 30 patients will do Post-bariatric body contouring procedure . Group (B): 30 patients as a control group will not do body contouring surgery.

Body Contouring Surgery will performed when the patient's weight has been stable within 5 kg for at least 3 months.

The Patients will have a fixed diet plan through the time of the study and diet will be given according to BMR

Men: $BMR = 88.362 + (13.397 \times \text{weight in kg}) + (4.799 \times \text{height in cm}) - (5.677 \times \text{age in years})$

Women: $BMR = 447.593 + (9.247 \times \text{weight in kg}) + (3.098 \times \text{height in cm}) - (4.330 \times \text{age in years})$

Weight and BMI documentation will occur after body contouring surgery before body contouring surgery and 3 and 6 months after.

Routine investigations (CBC, UR & CR, Lipid profile and RBS) will be done before body contouring surgery and 6 months after.

Measurement of post-bariatric body metabolism will be done by measurement of $TNF-\alpha$, hsCRP and BNP before body contouring surgery and 3 and 6 months after.

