Patient satisfaction score from 1 to 5 done 2 months post body contouring surgery. The weight of excised skin and fat in contouring surgery will be documented and removed from the net weight loss.

Inclusion criteria:

- Post-bariatric (sleeve) patients will do body contouring surgery.
- Post-bariatric patients has been stable within 5 kg for 3 months
- Age between 20-60 years old.
- patients use the determinant fixed diet.

Exclusion criteria:

- Age below 20 and above 60 years old.
- Non-compliance with the fixed diet.
- psychotic patients.
- Female patients seeking pregnancy.
- Endocrine causes of obesity.
- Bariatric surgery other than sleeve.

Procedures data:

- Demographic data
- Type of bariatric surgery
- Type of plastic operation
- Age of patient
- Timing of applying the methodology

Post-procedure data

- Weight changes
- Patients satisfaction score
- patient metabolism by hsCRP, TNF- α and BNP.

Evaluation of the patients:

1- patient weight and BMI:

Documentation of the patient weight and BMI after post-bariatric body contouring surgery for 6 months.

2- patient satisfaction score:

patient satisfaction score from 1 to 5 done 2 months post body contouring surgery.

Question	Score
How satisfied are you with the results of your surgery?	
Very satisfied	5
Somewhat satisfied	4
Neither satisfied nor dissatisfied	3
Somewhat dissatisfied	2
Very dissatisfied	1

3- Type of patient metabolism:

Detect patient metabolism by doing TNF- α , hsCRP and BNP before the body contouring surgery and 3 and 6 months after. Routine investigations (CBC, UR & CR, Lipid profile and RBS) will be done before body contouring surgery and 6 months after.

Statistical analysis

Statistical analysis was done by SPSS v26 (IBM Inc., Chicago, IL, USA). Quantitative variables were presented as mean and standard deviation (SD) and compared between the two groups utilizing unpaired Student's t- test. Qualitative variables were presented as frequency (%) and were analyzed utilizing the Chi-square test or Fisher's exact test when appropriate. A two tailed P value ≤ 0.05 was considered statistically significant.

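### The plan makes no provision for skewed hsCRP, TNF-alpha and BNP; if they are right-skewed, the raw-scale t-test at 30 per group loses power and is sensitive to a few high values

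*Combined protocol and SAP*

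**What the plan says.** The Statistical analysis section of the combined protocol and SAP is a single paragraph. For measured variables it states "Quantitative variables were presented as mean and standard deviation (SD" and that these are "compared between the two groups utilizing unpaired Student's t- test". The threshold is "A two tailed P value ≤ 0.05 was considered statistically significant". The paragraph offers a choice of test only for categorical data (Chi-square or Fisher's exact). It mentions no transformation, normality check, median, quartiles or rank-based test for quantitative data, and neither does any other section.

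The three markers are the plan's chosen measure of metabolism. Patients and methods introduces them with "Measurement of post-bariatric body metabolism will be done by measurement of", and Post-procedure data lists "patient metabolism by hsCRP" together with the other two. They are taken before contouring surgery and 3 and 6 months after it. The groups are small: "30 patients will do Post-bariatric body contouring procedure" and "30 patients as a control group will not do body contouring surgery".

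**The concern.** hsCRP, TNF-alpha and BNP are concentrations that cannot fall below zero, so a right-skewed distribution is a reasonable working assumption. hsCRP is also an acute-phase marker. Group A has an operation between baseline and follow-up and Group B does not, so a surgical wound problem could produce an isolated high value in Group A only. Intercurrent infection could do so in either group. With 30 patients per group, one such value can weigh heavily on both the mean and the SD.

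Metabolism is one of the two subjects in the study title. If the markers are skewed, that half of the question would be tested inefficiently, and the mean and SD would not describe a typical patient. A null result could then reflect the choice of scale rather than the absence of an effect.

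**Working it through.** **Figure to reproduce.** There is none. The documents give no effect size, SD, power or sample-size calculation; the 60 patients are simply 30 + 30.

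**Inputs from the documents.** 30 per group; two-sided 0.05; unpaired Student's t; mean and SD.

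**Inputs assumed.** Log-normal marker values with the same log-scale SD (s) in both groups; a constant ratio between groups; s from 0.3 to 1.2. None of these is in the documents.

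**Step 1: what 30 per group can detect.** By normal approximation, the standardised difference with 80% power is (1.960 + 0.842) × √(2/30) = 0.72. For the exact t-test, a difference of 0.736 SD has non-centrality 0.736 × √15 = 2.85 on 58 degrees of freedom, and power 80.0%. There is little power to spare.

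**Step 2: power on each scale.** The true effect is set at 0.736 s on the log scale, so the log-scale t-test always has 80%. The implied ratio is exp(−0.736 s). Skewness is (exp(s²) + 2) × √(exp(s²) − 1). There were 20,000 simulated trials per setting (5,000 for Mann-Whitney).

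| s | Skewness | Ratio | Raw t | Log t | Mann-Whitney | Raw t, type I error |
|---|---|---|---|---|---|---|
| 0.3 | 0.95 | 0.80 | 78% | 80% | 78% | 4.8% |
| 0.5 | 1.75 | 0.69 | 75% | 80% | 78% | 4.8% |
| 0.8 | 3.69 | 0.55 | 68% | 80% | 78% | 4.3% |
| 1.0 | 6.18 | 0.48 | 62% | 80% | 78% | 4.3% |
| 1.2 | 11.16 | 0.41 | 54% | 80% | 76% | 3.6% |

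Repeat runs of the raw-scale power agree to about one percentage point. The loss against the log scale is about 2, 5, 12, 18 and 26 points.

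**Step 3: change from baseline.** The plan does not say whether follow-up values or changes are compared. If changes are used, with an assumed log-scale correlation of 0.6 and the effect again set for 80% on the log scale, the raw test has 64%, 48%, 39% and 31% at s = 0.5, 0.8, 1.0 and 1.2.

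**Step 4: single high values.** The largest of 30 values supplies a median 21%, 27%, 36%, 41% and 47% of its group's sum of squares at the five values of s. As a direct test, the true ratio was set at 0.5 and one value of 30 in the lower group was multiplied by ten. At s = 0.5, raw-scale power falls from 99.8% to about 53%, while log-scale power stays at 99%. At s = 0.8 it falls from 81% to 39%, against 91% to 80% on the log scale.

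**Step 5: the summary.** With median 1 and s = 1.0, the mean is exp(0.5) = 1.65 and the SD is √((e − 1) × e) = 2.16. Mean minus one SD is 1.65 − 2.16 = −0.51, which is impossible for a concentration.

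**The case against.** The strongest reply is that the skewness is not documented. The plan gives no SD, range or assay for any of the three markers, and nothing shows that they share a similar spread. At s = 0.3 the loss is about 2 points, which nobody would act on. That stands, and it is why the size has to be given as a range.

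Second, log-normal data with a constant ratio are the ideal case for a log-scale t-test, so the comparison favours the remedy. This is partly right. The Mann-Whitney test, which does not depend on the log scale, still reaches 76 to 78% on the same data, and the single-spike test departs from the ideal model and points the same way.

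Third, the log scale does not rescue an underpowered comparison. With an assumed ratio of 0.75, power is 22% raw and 28% log at s = 0.8, and 13% and 19% at s = 1.0. That also stands.

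Fourth, a raw-scale t-test remains a legitimate test of a difference in arithmetic means, and moving to ratios changes the quantity estimated. This is true and belongs in the cost.

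A reader might infer that the planned t-test produces spurious findings. In these simulations it does not: its type I error is at or slightly below 5%. A reader might also want to add a substitution rule for values below an assay limit, or to treat triglycerides in the same way. The documents mention no assay limit and refer only to a lipid profile, so neither addition has support here.

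**Conclusion.** The gap is certain: one mean-and-SD rule with Student's t-test covers all quantitative variables, and nothing provides for skewed markers. That the analysis would be on the raw scale is the plain reading of the plan's silence on transformation.

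The harm is conditional. If the markers are right-skewed, the trial loses power and becomes sensitive to isolated high values. The loss from skew alone is slight for log-scale SDs of 0.3 to 0.5 and material from about 0.8. Sensitivity to a single extreme value is already marked at 0.5. The documents do not support saying that the markers are known to be skewed, that a large loss is certain, or that false positives are inflated.

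This should be changed because the remedy is cheap. It does not by itself invalidate the trial.

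**What to change.** Add to the Statistical analysis section: hsCRP, TNF-alpha and BNP will be analysed on the natural-log scale, adjusted for the log of the baseline value; results will be given as the ratio of geometric means between groups with a 95% confidence interval; raw values will be summarised by median and quartiles; a rank-based test will serve as sensitivity analysis.

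The baseline value is already in the measurement schedule. That schedule is timed from contouring surgery, so the text should state which measurement serves as baseline in Group B. Baseline adjustment is a further refinement; the case for the log scale does not depend on it.

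**Cost.** No new measurements are needed. Results become ratios rather than differences in arithmetic means. Timing matters: the document is dated 2026, the study is stated to run from 2021 to 2025, and the statistical paragraph is in the past tense. The documents do not say whether the data have been examined. If they have, the log-scale results must be labelled post hoc and shown alongside the planned t-test, not in place of it.

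### The only between-group method for outcomes measured three times is an unpaired t-test, so the 6-month result ignores the 3-month values of patients lost by then and can be biased if loss is outcome-related and differs between groups

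*Combined protocol and SAP*

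**What the plan says.** - **Design.** Patients and methods describes a non-randomised comparison: "This is a prospective comparative study on 60 patients", in Group A "30 patients will do Post-bariatric body contouring procedure", and in Group B "30 patients as a control group will not do body contouring surgery".
- **Schedule.** For weight and BMI: "Weight and BMI documentation will occur after body contouring surgery before body contouring surgery and 3 and 6 months after". The inflammatory and cardiac markers follow the same visits: TNF-alpha, "hsCRP and BNP before the body contouring surgery and 3 and 6 months after".
- **Analysis.** The Statistical analysis section states: "Quantitative variables were presented as mean and standard deviation (SD) and compared between the two groups utilizing unpaired" Student's t-test. The significance rule is "A two tailed P value ≤ 0.05 was considered statistically significant".
- **Diet.** A set diet runs for the whole study, and failure to keep to it is an exclusion criterion. The plan does not say whether that criterion can remove a patient after entry.
- **Not stated.** There is no repeated-measures or baseline-adjusted model, analysis set, expected loss, missing-data rule or sensitivity analysis. Nor does the plan say whether the t-test is applied to the value at a visit or to change from baseline.

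The satisfaction score (2 months) and the routine blood tests (before and at 6 months) follow other schedules and fall outside this point.

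**The concern.** An unpaired t-test takes one number per patient. At the last visit, a patient without a 6-month value contributes nothing, even if the 3-month value showed how that patient was doing. That the analysis will be confined to patients with a value is inferred from the method and from the plan's silence, but the text offers no other reading.

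Two routes could make the loss related to outcome and different between groups:

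1. Only Group A has an operation, so the reasons for returning may differ. Controls who are regaining weight might be the ones who stop attending.
2. If the diet exclusion is applied after entry, it removes patients for a reason tied to weight, which is itself an outcome.

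In the first case the remaining controls look better than the control group as a whole, and the 6-month difference is wrong. The 3-month values that could largely correct this are already scheduled for collection.

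**Working it through.** The plan has no figure of its own to reproduce: 60 patients is given without power, SD, effect size or loss.

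**Inputs from the documents.** 30 per group; visits before surgery and at 3 and 6 months; unpaired t-test; two-sided 0.05.

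**Assumptions (not in the documents).** True difference 0; SD of weight change 3.5 kg at 3 months and 5 kg at 6 months; correlation 0.7; 5% random loss in Group A; in Group B, loss more likely in those gaining at 3 months (log-odds 1 to 2 per SD).

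**Step 1: how the bias arises.** The slope of 6-month change on 3-month change is correlation × SD6 / SD3 = 0.7 × 5 / 3.5 = 1.0. Each kg by which the retained controls' mean 3-month change differs from that of all controls therefore passes in full into the 6-month comparison.

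**Step 2: simulated bias of the t-test on change.**

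| Group B loss | Bias (kg) | False positives |
|---|---|---|
| 10% | 0.3-0.5 | about 6-7% |
| 20% | 0.6-0.9 | about 7-10% |
| 30% | 0.9-1.3 | about 9-14% |

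A maximum-likelihood estimator that also uses the 3-month values had bias within about 0.03 kg throughout.

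**Step 3: hand check at 20% loss.** Expected numbers are 30 × 0.95 = 28.5 and 30 × 0.80 = 24. SE = 5 × √(1/28.5 + 1/24) = 1.385 kg. Bias/SE = 0.6/1.385 = 0.43 to 0.9/1.385 = 0.65. The chance that |Z + shift| exceeds 1.96 is then 7.2% to 10.0%, in line with the table.

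**Step 4: the same bias on raw 6-month weight.** Add an assumed baseline SD of 15 kg, unrelated to change. The 6-month SD is √(15² + 5²) = 15.8 kg and SE = 15.8 × √(1/28.5 + 1/24) = 4.38 kg. Bias/SE is at most 0.9/4.38 = 0.21, giving about 5.5%. Simulation across the settings gave 4.6-6.4%. The bias in kg is similar, but the false-positive rate barely moves.

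**Step 5: which loss patterns matter.** A separate simulation in SD units (correlation 0.5 or 0.7, true difference 0):

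| Loss A / B | Type of loss | Bias (SD) | Type I error |
|---|---|---|---|
| 10% / 30% | random in both | 0.002-0.003 | 5.0-5.1% |
| 20% / 20% | outcome-related in both | -0.002 to -0.004 | 5.3-6.2% |
| 0% / 10% | outcome-related in B | 0.07-0.09 | 5.8-6.8% |
| 0% / 20% | outcome-related in B | 0.13-0.19 | 7.3-11.7% |
| 10% / 30% | random in A, outcome-related in B | 0.21-0.28 | 11.1-16.8% |

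Loss has to be both outcome-related and different between groups before the difference moves.

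**Step 6: why the covariance matters in the replacement model.** Under the assumptions above, the variance of change is 3.5² = 12.25 from baseline to 3 months, 5² = 25 from baseline to 6 months, and 25 + 12.25 - 2 × 0.7 × 3.5 × 5 = 12.75 from 3 to 6 months. A random intercept alone forces these three to be equal, at about (12.25 + 25 + 12.75)/3 = 16.7. This has two effects:

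- The SE for 6-month change is too small by a factor √(16.7/25) = 0.82. The nominal 1.96 becomes 1.96 × 0.82 = 1.60, which is about 11% false positives before any loss.
- With a large between-patient SD, the model predicts a lost patient's 6-month weight from roughly the average of the two earlier values. That is a slope of about 0.5 on 3-month change instead of 1.0, so about half the bias remains.

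Simulation agreed: residual bias was 0.13-0.26, 0.33-0.48 and 0.44-0.68 kg at 10, 20 and 30% control loss, with 11-15% false positives. An unstructured covariance imposes no such equality.

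**The case against.** The strongest reply is that the mechanism is assumed. The documents give no loss rate and do not say that controls attend less or are followed by another team. Both groups appear to be on the study diet, which implies some contact with controls. Matching includes length of follow-up, which might limit uneven follow-up, although it may refer only to time since bariatric surgery. All of this stands. It limits what can be said about size, but it does not supply a rule for patients with no 6-month value.

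Three stronger readings are tempting and are not supported:

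- *A reader might infer that unequal loss by itself biases the result.* It does not: random loss of 10% against 30% left the difference unbiased.
- *A reader might infer that the false-positive rate will generally exceed 5%.* That holds for change scores under the assumed SDs. The plan lists weight changes among its data but does not say which quantity is tested, and on raw 6-month weight the inflation is small.
- *A reader might infer that any mixed model cures the problem.* A random intercept alone left about half the bias here, with more false positives than the change-score t-test in most settings.

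At 10% control loss the effect on false positives is also modest.

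**Conclusion.** The concern holds in conditional form. The plan names a method that discards the 3-month information on patients without a 6-month value, and it says nothing about how such patients are handled. If their loss is related to outcome and differs between groups, the 6-month difference can be biased. Under the stated assumptions the bias is a fraction of a kilogram at 10% control loss and about 1 kg at 30%.

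These figures illustrate sensitivity; they do not predict this study's error, because the loss rates, SDs, correlation and dropout mechanism are all absent from the documents. They are also for weight only; no comparable figure can be given for the markers. The change is worth making because it is cheap, not because bias has been shown. Confidence is medium.

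**What to change.** For each outcome measured at all three visits, replace the separate t-tests with one repeated-measures linear mixed model in SPSS v26, the package already named. Use terms for group, visit and group-by-visit, and an unstructured covariance across visits rather than a random intercept alone. Then:

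1. Include every enrolled patient with any value, including those who break the diet, and state whether the diet exclusion applies only at entry.
2. Name the group contrast in 6-month change from baseline as the result. For weight, apply the protocol's existing adjustment for excised tissue.
3. Report the number measured per group at each visit, with reasons for loss.
4. Add one sensitivity analysis in which lost controls are assumed to do worse.

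The cost is SAP wording and a little more analysis, with no new data. The model assumes that loss depends only on values already observed; this is weaker than what the completer t-test needs but cannot be verified, hence item 4. The model deals with missing visits only. It does not remove confounding from the non-randomised comparison, and as specified it does not use the 1:1 matching.

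### Controls are matched 1:1, but the only tests named are for independent samples with no adjustment for the matching factors, so precision is lost if matched outcomes are positively correlated

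*Combined protocol and SAP*

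**What the plan says.** Under Patients and methods, the combined protocol and SAP describes "This is a prospective comparative study on 60 patients". It says of the contouring patients: "This cohort of patients was then matched and compared with a 1:1 control group". The factors are listed: "Matching will be based on age, gender, BMI at the time of bariatric surgery, type of bariatric surgery procedure, and length of follow-up". The group sizes follow: "30 patients will do Post-bariatric body contouring procedure" and "30 patients as a control group will not do body contouring surgery".

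Under Statistical analysis, quantitative variables are "compared between the two groups utilizing unpaired" Student's t-tests. Qualitative variables "were analyzed utilizing the Chi-square test or" Fisher's exact test. The level is 0.05, two-sided, and the planned summaries are means and SDs. These are the only inferential methods named: there is no paired test, no conditional or mixed model, and no covariate adjustment. The plan gives no pairing procedure, caliper or pair identifier.

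**The concern.** An independent-samples test takes the 30 contouring patients and the 30 controls to be unrelated. If each control was chosen to resemble one contouring patient in age, sex and starting BMI, the outcomes of the two may be alike, most plausibly for absolute weight and BMI. The difference between the group means then varies less than the unpaired formula assumes.

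What is at stake is precision. Matching would have taken effort to do and its gain would not be collected. The study is small and the plan gives no sample-size calculation, so a non-significant result could owe something to the test rather than to the surgery.

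**Working it through.** **Inputs from the documents.** n = 30 per group, 1:1 matching, unpaired t-test, two-sided level 0.05.

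**Assumptions.** The within-pair correlation ρ is not in the documents and is shown over a range. Outcomes are taken as normal with equal SD σ in the two groups. A difference of 0.5 SD serves as an illustration.

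**Plan's own figure.** There is none to reproduce: no power, effect size or SD is stated. As a benchmark, 30 per group with an unpaired t-test and ρ = 0 gives 80.5% power for a difference of 0.74 SD and 47.8% for 0.5 SD.

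**Standard error.** The unpaired test estimates σ√(2/n) = σ√(2/30) = 0.258σ. With pairs, the true value is σ√(2(1−ρ)/n). The ratio is 1/√(1−ρ); at ρ = 0.3 it is 1/√0.7 = 1.195.

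**Interval width.** The unpaired 95% interval uses t(58) = 2.002 and the paired one t(29) = 2.045. The width ratio is (2.002/2.045)/√(1−ρ), a little below the standard-error ratio; at ρ = 0.3 it is 0.979 × 1.195 = 1.17.

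**Type I error of the unpaired test.** Approximately 2(1 − Φ(1.96/√(1−ρ))), which gives 0.039, 0.028, 0.019 and 0.006 at ρ = 0.1, 0.2, 0.3 and 0.5. The table shows the results of simulating 100,000 trials per value of ρ.

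**Power at 0.5 SD.** The paired test uses the non-central t with 29 df and non-centrality 0.5/√(2(1−ρ)/30): 1.94 at ρ = 0 and 2.74 at ρ = 0.5. Power of the unpaired test is simulated.

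| Assumed ρ | SE ratio | 95% interval ratio, unpaired to paired | Type I error, unpaired | Power, unpaired | Power, paired |
|---|---|---|---|---|---|
| 0 | 1.00 | 0.98 | 5.0% | 47.8% | 46.5% |
| 0.1 | 1.05 | 1.03 | 3.9% | 47.8% | 50.5% |
| 0.2 | 1.12 | 1.09 | 2.9% | 47.4% | 55.3% |
| 0.3 | 1.20 | 1.17 | 2.0% | 47.6% | 60.9% |
| 0.5 | 1.41 | 1.38 | 0.7% | 47.0% | 75.4% |

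The simulated type I error of the paired test was 4.9% to 5.1% in every row. The two tests have equal power at ρ of about 0.03 to 0.04.

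**Qualitative variables.** With a 30% event rate in both groups, the type I error of the chi-square test is 2.8%, 1.9% and 0.6% at ρ = 0.2, 0.3 and 0.5, which is the same pattern.

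**The case against.** The documents never mention pairs. A 1:1 ratio suits individual matching, but the same section goes on to speak of dividing the patients into two groups, so balancing at group level is possible. A paired test would then not be available. This stands, and it is why the fix has two branches.

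The correlation could also be small. Procedure type is constant, because the Exclusion criteria admit only sleeve patients, so it adds no correlation. BMI is matched at bariatric surgery, whereas the outcomes (weight change, TNF-α, hsCRP and BNP) are measured around later contouring. At ρ = 0 the planned test is valid and slightly the more powerful. This stands too: the mismatch is certain, its size is not.

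A reader might infer more than the documents support:

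- **That the P values are simply wrong, or that false positives are inflated.** With positive correlation the error is conservative. Only a negative correlation would inflate type I error (7.4% at ρ = −0.2), and matching would not be expected to produce one.
- **That the reported error bars are wrong.** The plan mentions none. It reports SDs, which pairing does not change.
- **That the matching is wasted.** Any balance it achieves still limits confounding in the unpaired mean difference.
- **That the qualitative tests are equally affected.** The named outcomes are mostly continuous, and the satisfaction score asks about the patient's own surgery, so controls have no counterpart.

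**Conclusion.** The mismatch between a 1:1 matched design and an unadjusted independent-samples analysis is real, and nothing else in the documents cures it. If matching formed pairs with positively correlated outcomes, the group comparison is less precise than it need be. At correlations of 0.3 to 0.5, a paired test would gain about 13 points (60.9 − 47.6) to 28 points (75.4 − 47.0) of power for a 0.5 SD difference. At 0.1 the gain is about 3 points, and at zero there is a loss of about 1. These figures rest on an assumed correlation, normal outcomes and 30 complete pairs. A significant result under the planned test would not be called into question by a positive correlation. Severity: should be fixed, not critical.

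**What to change.** First state whether matching formed individual pairs.

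- **If it did:** replace the unpaired t-test with a paired t-test on within-pair differences, or with a linear mixed model that has a random effect for pair. Carry a pair identifier in the dataset.
- **If matching was only at group level:** use a regression (ANCOVA) adjusting for the baseline value, age, sex, BMI at bariatric surgery and length of follow-up. Procedure type is left out because it does not vary.
- **Qualitative outcomes:** use McNemar's test or conditional logistic regression only for a binary outcome measured in both members of a pair. Do not apply either to the satisfaction score.

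The cost is SAP wording and one extra variable. No patients or visits are added, and SPSS can fit these models. A simple paired test has 29 degrees of freedom instead of 58, and a pair with one member missing drops out of it; the mixed model can keep the remaining member. The ANCOVA with these five covariates leaves 60 − 7 = 53 residual degrees of freedom. The Statistical analysis section is written in the past tense, so if results have already been produced, the change should be reported as a revision of the plan.
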